- 266 • Live within 120 minute radius of Massachusetts General Hospital
- 267 • Willing to remain within a 250 mile radius of the central monitoring location during the outpatient run-
268 in period. No air travel will be allowed, and subjects will still be expected to follow the visit schedule as
269 described.
- 270 • Willing to spend the night prior to both exercise visits in a hotel and fast overnight prior to exercise
- 271 • Willing and able to avoid deodorant, scented lotions, and scented laundry detergent on your clothes on
272 the days of the exercise visits
- 273 • Willing to wear two steel cannula infusion sets (6 mm Contact Detach) and one Dexcom CGM sensor and
274 change sets frequently (a new glucagon infusion set daily and a new insulin infusion set every other day
275 during the outpatient run-in period)
- 276 • Have a mobile phone they will have access to at all times during the outpatient run-in period for making
277 contact with study staff

278
279 No subjects will be excluded on the basis of gender or race. The requirement that subjects manage their diabetes
280 using subcutaneous insulin infusion pump therapy is imposed because multiple daily injection therapy involves
281 the use of long-acting basal insulin that would require an extended washout period.
282

283 **III. b. Exclusion Criteria**

- 284 • Unable to provide informed consent (e.g. impaired cognition or judgment)
- 285 • Unable to safely comply with study procedures and reporting requirements (e.g. impairment of vision or
- 286 dexterity that prevents safe operation of the bionic pancreas, impaired memory, unable to speak and
- 287 read English)
- 288 • Current participation in another diabetes-related clinical trial that, in the judgment of the principal
- 289 investigator, will compromise the results of this study or the safety of the subject
- 290 • Pregnancy (positive urine HCG), breast feeding, plan to become pregnant in the immediate future, or
- 291 sexually active without use of contraception
- 292 ○ Subjects must use acceptable contraception for the two weeks prior to the study, throughout the
- 293 study and for the two weeks following the study.
- 294 ○ Acceptable contraception methods include:
- 295 ▪ Oral contraceptive pill (OCP)
- 296 ▪ Intrauterine Device (IUD, hormonal or copper)
- 297 ▪ Male condoms
- 298 ▪ Female condoms
- 299 ▪ Diaphragm or cervical cap with spermicide
- 300 ▪ Contraceptive patch (such as OrthoEvra)

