- 329 reassuring evaluation by a cardiologist after an abnormal EKG finding may allow participation.
- 330 • Congestive heart failure (established history of CHF, lower extremity edema, paroxysmal nocturnal

- 331 dyspnea, or orthopnea)
- 332 • History of TIA or stroke
- 333 • Seizure disorder, history of any non-hypoglycemic seizure within the last two years, or ongoing treatment
- 334 with anticonvulsants
- 335 • History of hypoglycemic seizures (grand-mal) or coma in the last year
- 336 • History of pheochromocytoma: fractionated metanephrines will be tested in patients with history
- 337 increasing the risk for a catecholamine secreting tumor:
- 338 ○ Episodic or treatment refractory (requiring 4 or more medications to achieve normotension)
- 339 hypertension
- 340 ○ Paroxysms of tachycardia, pallor, or headache
- 341 ○ Personal or family history of MEN 2A, MEN 2B, neurofibromatosis, or von Hippel-Lindau disease
- 342 ○ Adrenal tumor that has not undergone characterization for endocrine function
- 343 • Hypertension with systolic BP ≥ 160 mm Hg or diastolic BP ≥ 100 despite treatment
- 344 • History of any orthopedic conditions rendering exercise unsafe
- 345 • Untreated or inadequately treated mental illness (indicators would include symptoms such as psychosis,
- 346 hallucinations, mania, and any psychiatric hospitalization in the last year), or treatment with anti-
- 347 psychotic medications that are known to affect glucose regulation.
- 348 • Electrically powered implants (e.g. cochlear implants, neurostimulators) that might be susceptible to RF
- 349 interference
- 350 • Unable to completely avoid acetaminophen for duration of study
- 351 • History of adverse reaction to glucagon (including allergy) besides nausea and vomiting
- 352 • Any known history of hypersensitivity to lactose
- 353 • Established history of allergy or severe reaction to adhesive or tape that must be used in the study
- 354 • History of eating disorder within the last 2 years, such as anorexia, bulimia, or diabulemia or omission of
- 355 insulin to manipulate weight
- 356 • History of intentional, inappropriate administration of insulin leading to severe hypoglycemia requiring
- 357 treatment
- 358 • Use of oral (e.g. thiazolidinediones, biguanides, sulfonylureas, glitinides, DPP-4 inhibitors, SGLT-2
- 359 inhibitors) or non-insulin injectable (GLP-1 agonists, amylin) anti-diabetic medications

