521 **Treadmill:** The study will utilize a treadmill for the exercise visit at the end of each study arm. The treadmill will
522 be stored in the Diabetes Research Center when not in use.

523 524 **V. d. Experimental Procedures and Data Collection**

525 **V. d. i. Screening Visit**

- 526 • All subjects will have a screening visit to confirm eligibility. Informed consent will be obtained and

527 documented with a signed informed consent document before any trial-related procedures are
528 conducted.

- 529 • The subject will be interviewed and the case report form will be completed by study staff to establish
530 whether the subject is eligible to continue with the screening.
- 531 • A urine pregnancy test will be performed in female volunteers. If the test is positive the volunteer will be
532 informed of the result and the visit will be ended.
- 533 • Height, weight and blood pressure will be measured. An EKG will be performed in subjects who are either
534 ≥ 50 years of age or who have had diabetes for ≥ 20 years.
- 535 • If the volunteer is not excluded based on historical criteria, blood pressure, EKG or urine pregnancy test,
536 blood will be drawn for hemoglobin and hemoglobin A1c. Plasma fractionated metanephrines may be
537 obtained if indicated by history.
- 538 • Once all of the laboratory results have been returned, a study MD or NP will review the case report form
539 to determine subject eligibility. If subjects are not eligible to continue in the study the results of abnormal
540 tests will be reported to the subjects and to a health care provider of their choosing.
- 541 • Subjects who have been screened and are eligible can participate without having to be re-screened for a
542 period of one year. The study staff should verbally confirm that there have been no health events that
543 would make them ineligible if the interval between screening and participation is longer than 3 months.
544

545 **V. d. ii. Randomization of Study Visit Order:** Once the subject has been enrolled and eligibility of subjects has
546 been established, subjects will be randomized to one of the possible two visit-orders. In random order, subjects
547 will complete an insulin only exercise visit and a bi-hormonal exercise visit. The outpatient run-in period for both
548 exercise visits will use the bi-hormonal bionic pancreas.

549
550 **V. d. iii. General Study Policies during the Outpatient Run-In:**

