- 636 and to resolve problems with network coverage. If there are no indications of device
- 637 malfunction as the cause for lost connectivity, the glucose level is in safe range, and a subject
- 638 chooses to remain in an area with poor network coverage, we will instruct the subject to
- 639 check the bionic pancreas display at least every 30-60 minutes for alert icons. We will call
- 640 the subject every 2 hours to check on safety and device function until remote monitoring is
- 641 restored.
- 642 ● If there is a technical problem with the bionic pancreas that cannot be resolved over the phone, a
- 643 member of study staff may be dispatched to the location of the subject to provide in-person
- 644 assistance. The subject may be asked to come to the Diabetes Research Center or study staff may
- 645 meet them in another public place. If this is not possible or would be too disruptive (i.e. in the middle
- 646 of the night) the subject will be asked to take over their own glycemic control using their insulin pump
- 647 until such time as a meeting can be arranged for in-person inspection of the device. This should occur
- 648 in most cases within 12 hours. Staff will not go into subjects' houses or other non-public places, nor
- 649 will they go to any place to meet the subject that is not public or where they do not feel safe.

651 **V. d. v. Visit Procedures**

652 **Visit 1:**

- 653 ● On arrival to the first study visit, the body weight of the subject will be documented.
- 654 ● A urine pregnancy test will be performed in female volunteers at the start of the first arm. If the test is
- 655 positive the volunteer will be informed of the result and the visit will be ended. The date of the last
- 656 menstrual period will also be documented, along with usual cycle length, for female subjects.
- 657 ● The subjects will place a Dexcom G5 sensor and study staff will confirm they are doing it properly.
- 658 ● Study staff will provide supplies and review the study procedures again. Study staff will supervise the
- 659 setup of the insulin and glucagon pumps and infusion sets.
- 660 ● The control algorithm will be initialized only with the subject's weight. Diagnostics will be performed to
- 661 ensure that the Dexcom CGM device is appropriately calibrated and that all of the components of the
- 662 bionic pancreas are in good communication with each other.

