 - Subjects will have the option to begin the next arm of the study on the same day they complete the first arm. If subjects choose this option, they will start over with Visit 1 procedures.
 - If the subject has chosen to complete their second study arm at a later date or has completed both study arms, they will resume their usual care on their own insulin pump, and study staff will review the last several hours of insulin and/or glucagon dosing with them.

834
835
836
837
838
839
840
841
842
843
844
845
846
847
848
849
850
851
852
853
854
855
856
857
858
859

V. d. vi. Response to Hypoglycemia

- While wearing the bionic pancreas at home, subjects are encouraged to check their BG for any symptoms of hypoglycemia.
- Subjects are encouraged to treat hypoglycemia according their usual practice or according to the “rule of 15s”: take 15 grams of rapid acting carbohydrate and recheck in 15 minutes, then repeat as needed.
- Subjects will be instructed to check their glucagon infusion site and their bionic pancreas for normal operation any time hypoglycemia occurs. If there is any suspicion of glucagon infusion set malfunction, the site should be replaced.
- If a subject experiences a seizure or unconsciousness associated with hypoglycemia in the study, his or her participation in the study will be discontinued.

V. d. vii. Response to Hyperglycemia

- Subjects will be instructed to check their insulin infusion site and their pump or bionic pancreas for normal operation any time BG is greater than 300 mg/dl. If there is any suspicion of insulin infusion set malfunction, the site should be replaced.
- Subjects may contact a study provider (MD or NP) for advice at any time, and may contact the troubleshooting support team, as they wish. During both study arms, subjects will be assisted in checking the bionic pancreas for any malfunction and correcting any problems that are found.
- If no correctable fault is found, but there is doubt regarding the correct function of the bionic pancreas system, an entirely new backup bionic pancreas system may be brought to the subject's location by study staff.
- If a subject experiences diabetic ketoacidosis requiring hospitalization during the study, his or her participation in the study will be discontinued.

V. d. viii. Response to Nausea/Vomiting

860

861 If significant nausea, nausea that prevents the subject from eating normally, or any vomiting occurs during either

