1069 leading to significant harm to volunteers is expected to be very low. A small meal or snack will be made available
1070 to subjects after completion of the study.

1071

1072 Subjects may experience discomfort with insertion of the peripheral intravenous line, infusion sets, and Dexcom
1073 sensor into the subcutaneous tissues. The risk of discomfort due to insertion of infusion sets and Dexcom sensors

1074 may be greater than in their lives outside the trial because more infusion sets and sensors will be inserted than
1075 they may be used to.

1076

1077 There is a risk of risk of dizziness or lightheadedness from blood loss. However, typical blood loss will be limited
1078 to no more than 216 ml. Exclusion of subjects with anemia will help mitigate this risk.

1079

1080 There is a risk of headache, nausea, or vomiting in subjects due to the administration of exogenous glucagon.
1081 There is a possible risk of skin rash due to administration of exogenous glucagon. There may be risks of daily,
1082 low-level glucagon administration that have not become apparent during trials lasting up to 11 days. One
1083 possible risk is weight loss although no changes in weight have been observed in trials lasting up to 11 days.
1084 Others may include changes in blood chemistries or blood counts. The magnitude of the other possible risks due
1085 to daily administration of small amounts of glucagon are unknown, but are not expected to be high because
1086 mean glucagon levels have been in the normal fasted range in previous trials and there have be no other adverse
1087 events in previous bionic pancreas trials lasting up to 11 days. Of note, the incidence of nausea or vomiting has
1088 been low in prior studies and in one randomized double-blinded placebo controlled study it was not different
1089 from placebo.

1090

1091 **VIII. Potential Benefits**

1092

1093 Based on evidence from previous trials of the bionic pancreas and the design of this trial, subjects enrolled in the
1094 study may benefit from a reduction in risk of hypoglycemia and hyperglycemia and a better mean glucose during
1095 the outpatient run-in period.

1096

1097 Additionally, this study will help us to identify the utility of microdose glucagon in a bionic pancreas to prevent
1098 and treat hypoglycemia in the context of exercise, and FDA CDER has indicated that PG data demonstrating this

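### After screening, a pregnancy test is required only when the first arm begins, and the verbal eligibility check is not clearly tied to either arm, although the second arm repeats the same exposure

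*Combined protocol and SAP*

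**What the plan says.** **Exclusion.** Section III.b excludes "Pregnancy (positive urine HCG), breast feeding, plan to become pregnant in the immediate future, or" sexual activity without contraception. Contraception must cover the two weeks before the study, the study itself and the two weeks after it.

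**Screening (V.d.i).** A urine pregnancy test is done. The screening result then stands: "Subjects who have been screened and are eligible can participate without having to be re-screened for a" "period of one year. The study staff should verbally confirm that there have been no health events that" would make a subject ineligible. That confirmation is required only when more than 3 months lie between screening and participation.

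**Visit 1 (V.d.v).** "A urine pregnancy test will be performed in female volunteers at the start of the first arm". A positive result ends the visit.

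**Second arm (V.d.v, Exercise Visits).** There are two routes. A subject may begin the second arm on the day the first ends, and then goes through the Visit 1 procedures again. The other route is a delayed start: "If the subject has chosen to complete their second study arm at a later date or has completed both" arms, the subject goes back to usual care on their own pump. Nothing is said about checks on return, or about how long the gap may be.

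**Criteria with a time window.** III.a requires a prescription regimen stable for more than 1 month, apart from drugs the principal investigator judges irrelevant to safety and outcomes. III.b looks back 30 days for alcohol, 6 months for other substances and a year for psychiatric admission, and excludes "History of hypoglycemic seizures (grand-mal) or coma in the last year".

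**The concern.** The two arms expose the subject to the same things. Each has an outpatient run-in on the bi-hormonal device, always with glucagon, followed by a fasted exercise session that section VII describes as intended to bring on hypoglycemia. A check that protects the subject before the first exposure is needed for the same reason before the second.

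As written, a woman whose second arm starts weeks or months after the first can go through it with no test since the first arm began. A subject whose medication changed, or who had a disqualifying event, between a valid screening and an early first arm meets no scheduled question at all. Neither case would be a protocol deviation. The stake is subject protection and control of eligibility, not the statistical inference.

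**Working it through.** The plan gives no figure on this point to reproduce. The check sets the sections side by side and works out the intervals they allow.

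**1. Age of the latest pregnancy test at each exposure.** Inputs: run-in of 24 to 96 hours per arm (V.d.v, Exercise Visits) and the test timing above. Clinic hours are ignored.

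| Exposure | What the text requires | Age of latest test |
|---|---|---|
| First arm, Visit 1 | Test | 0 days |
| Second arm, same-day start, Visit 1 | Exercise Visits: repeat Visit 1 procedures. Visit 1: test belongs to the first arm | 0 days if repeated; otherwise 24 to 96 h = 1 to 4 days |
| Second arm, same-day start, exercise visit | As above | If not repeated: (24 + 24) to (96 + 96) = 48 to 192 h = 2 to 8 days |
| Second arm, later start | Nothing stated | No maximum given in V.d.v |

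For a same-day start the conflict matters little in practice. The gap is in the last row.

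**2. Outer limit for the last row.** If the one-year validity in V.d.i also governs the second arm, that arm must fall within a year of screening. If it governs only entry to the first arm, the only guide is section IV.a, which expects experiments and analysis to take 6 to 12 months. Either way, a gap of months is possible.

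**3. The verbal confirmation.** Take an assumed schedule for illustration: screening at week 0, first arm at week 10, second arm at week 20. Three months is 3 × 52/12 = 13 weeks.

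- If participation means the first arm: 10 < 13, so no confirmation is required before either arm.
- If it means each arm: none is required before the first (10 < 13), and one is required before the second (20 > 13).
- If it means each arm but the second is at week 12: none is required before either.

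On every reading, a first arm within 3 months of screening has no scheduled check.

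**4. Against the medication window.** On the same schedule, suppose a relevant prescription changed at week 8. At the first arm the regimen has been stable for 10 − 8 = 2 weeks, short of the required more than 1 month, and no question is due. This happens because the unchecked period (3 months) is longer than the window it should protect (more than 1 month).

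**5. The protocol's own logic.** Contraception is required throughout and screening already includes a test. The protocol still tests again when the first arm begins. It therefore treats neither contraception nor an older negative result as enough before exposure. Nothing in the text explains why the second arm should differ.

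**The case against.** Much of the case on the other side stands, and it limits the point.

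- **Pregnancy is tested more than once.** A reader might infer a single check. There are two, at screening and when the first arm begins, so first-arm exposure is covered.
- **The affected share is unknown.** A reader might count 20 subjects × 2 visits = 40 and call half of them, 20, untested. That would include men, women to whom the test does not apply (V.a and VI.a.1 list it for pre-menopausal females) and same-day starts. The documents do not support the figure.
- **The second arm may not be open-ended.** V.d.v states no maximum gap, but a second arm is participation in the ordinary sense, so the one-year validity and the 3-month rule may reach it. The text is ambiguous here, which is not the same as setting no limit.
- **A verbal check suits the history items.** Seizure, admissions, substance use and medication are taken by interview at screening too. The weakness is when the question is asked, not that it is verbal.
- **Hemoglobin.** Section VII says of blood loss: "Exclusion of subjects with anemia will help mitigate this risk". A reader might infer that the screening value must be repeated after 3 months. The documents set that interval for a verbal check, not for laboratory results, and give no basis for a fixed repeat rule.
- **Other safeguards exist.** The investigator may exclude for any safety factor (III.b), sedating drugs can end participation (V.d.iii), intercurrent illness can lead to removal (IX.b), and a nurse or physician supervises the exercise visit (VII). A hypoglycemic seizure in the study ends participation (V.d.vi).

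These safeguards are not scheduled re-checks. The discretionary ones work only if someone learns of the change, and the seizure rule does not find an event between screening and the first arm. None of them puts a pregnancy test before a delayed second arm.

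**Conclusion.** The point holds in a limited form. After screening, the only pregnancy test clearly required is at the first arm. For a same-day second arm, two parts of V.d.v contradict each other. For a later one, no test is stated. The verbal confirmation is not required for intervals of 3 months or less, and its reference arm is undefined.

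The size in subjects or visits cannot be derived: the documents give neither a sex or age split nor the expected share of delayed second arms. For a same-day start, the latest test is at most about 4 days old at the second Visit 1. For a delayed start it could be months old.

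The conclusion assumes that the eligibility criteria are meant to hold at exposure and not only at screening. V.d.i supports this, because its verbal check would otherwise have no purpose. The test size of 0.025, the power table and the McNemar analysis do not depend on any of this. It is a safety and eligibility-control gap that should be closed because closing it costs very little.

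**What to change.** Make two changes to the text.

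1. **V.d.v.** Reconcile Visit 1 with Exercise Visits so that the urine test is done at the start of each arm, for same-day and later second arms alike. State to whom it applies: V.a and VI.a.1 say pre-menopausal females, while V.d.i and V.d.v say female volunteers.
2. **V.d.i.** Require the existing verbal confirmation at Visit 1 of both arms, whatever the interval since screening. Word it to cover the time-windowed criteria: medication stability, seizure or coma, alcohol and substance use, and psychiatric admission. Say whether the one-year validity runs to the first arm or the second.

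The cost is one extra urine test per applicable woman and a short checklist per arm. No new visit appears to be needed: the payment total in section X implies ($225 − $25) / $50 = 4 study visits, which fits a Visit 1 and an exercise visit in each arm.

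The downside is an occasional late finding of ineligibility. A subject lost between arms would contribute one exercise visit and fall under the existing provision for such subjects in section VI. The enrollment ceiling of 40 for 20 completers (IV.a) leaves room to replace them.
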